- Days 1, 8, 15 and 29 require sample collection for performing laboratory tests and will be conducted at the site or via home visit.
- Any in-person visit may also have telemedicine or telephone components if all study activities cannot be completed in person.
- The visits that include bloodwork must be conducted at the study site or arrangements made for sample collection at the subject's home or other appropriate location.
- Site staff (in case of an in-person visit) or subjects (in case of a remote visit) will assess respiratory rate, heart rate, body temperature and SpO₂ (a thermometer and pulse oximeter are to be provided to subjects who are home quarantined, leave the hospital or are unable to return for study visits).
- Subjects will record details of concomitant medications, adverse events in the patient diary card (PDC).
- Subjects will complete a symptom assessment form on designated days daily during the study period (days 1 – 8, 12, 15, 22, and 29).
- In case the subject is hospitalized during the course of study, the activities specified in scheduled visits / time points will be carried out within the hospital facility.
- Study completion or the reason for study discontinuation will be recorded in the source document and the eCRF.

DSMB Meeting:

A Data Safety Monitoring Board (DSMB) will meet to review the safety and scientific conduct of the study. At a minimum, the DSMB will review the protocol and study design prior to study start, after the end of the first part of the study prior to the expansion phase, and at the end of the study.

Protocol for clinical study of Brequinar

Protocol No.: 21-VIN-0372

Version No.: 2.1; Dated: 29 Dec 2021

Supersedes: 02; Date of Supersedes: 30 Sep 2021

At each interim meeting the DSMB members will determine whether to stop the study, amend the protocol, or continue the study per protocol. The study enrollment will not be suspended for routine DSMB meetings.

The DSMB will be convened and enrollment suspended if Cohort-Level Stopping Criteria are met. The DSMB may allow the enrollment to resume following their review if safety criteria are met.

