12.9 Handling and Reporting of Adverse Events

An adverse event is any untoward medical occurrence (including a symptom or disease or an abnormal laboratory finding) during treatment with an investigational drug or a pharmaceutical product in a subject that does not necessarily have a relationship with the treatment being given.

*Abnormalities based on laboratory parameters, vital signs, and 12-Lead ECG will be called AE, if they are associated with at least one of the following:

- Interruption or stoppage of the study medication
- Associated with signs or symptoms
- Requiring treatment
- Considered clinically significant by the investigator

Safety Criteria:

An independent, unblinded study physician (from CRO) will assess each cohort for safety. A cohort will be declared safe as soon as all results are available for the Day 15 visit if the following conditions are met:

- No toxic deaths (deaths judged by the investigator to be related to either study drug);
- Not more than 1 toxic SAE (SAEs judged by the investigator to be related to either study drug);
- No Grade 3 or higher toxicities (including laboratory AEs as per CTCAE version 5.0 or higher) (AEs judged by the investigator to be related to either study drug);
- <4 subjects with any grade toxicity (AEs judged by the investigator to be related to either study drug).

In addition to the cohort-level safety, the independent study physician (from CRO) will determine if any subjects meet Individual Stopping Criteria:

- Subjects who develop a Grade 3 toxicity that is assessed by the investigator to be related to the study drug are to be permanently discontinued from study treatment but will continue in the study for safety assessments.
- Subjects who develop a Grade 4 toxicity, regardless of relatedness to study drug, are to be permanently discontinued from study treatment but will continue in the study for safety assessments.

In addition to the individual subject-level safety, the independent study physician (from CRO) will determine if a cohort meets Cohort-level Stopping Criteria prior to completing the 16 subjects, in which case no additional subjects will be enrolled into that cohort and no higher brequinar doses will be assessed:

Protocol for clinical study of Brequinar

Protocol No.: 21-VIN-0372

Version No.: 2.1; Dated: 29 Dec 2021

Supersedes: 02; Date of Supersedes: 30 Sep 2021

- ≥ 3 brequinar-treated or combination-treated subjects meet the individual stopping criteria.

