- ≥ 5 brequinar-treated or combination-treated subjects develop a Grade 3 or higher AE regardless of relationship to study drug.

Adverse Drug Reaction is a noxious and unintended response to a medicinal product related to any dose. The phrase responses to a medicinal product means that a causal relationship between a medicinal product and an adverse event is at least a reasonable possibility, i.e. the relationship cannot be ruled out. Regarding marketed medicinal products: a response to a drug which is noxious and unintended and which occurs at doses normally used in man for prophylaxis, diagnosis, or therapy of diseases or for modification of physiological function.

An **Unexpected Adverse Drug Reaction (UADR)** is an adverse reaction, the nature or severity of which is not consistent with the applicable product information [e.g., investigator's brochure for an unapproved investigational medicinal product or company core data sheet or package insert for marketed product].

Subjects will be monitored throughout the study period for adverse events. Subjects will be instructed to bring to the notice of study personnel any adverse event that may occur during the entire study period.

The following information is to be recorded for each adverse event individually in Adverse Event Reporting Form.

- Type of adverse event*
- Is it serious or non-serious?
- Date of onset/reporting
- Date of onset and resolution
- Severity (as per section 12.12)
- Association with the study medication (as per section 12.13)
- Action taken
- Outcome of adverse event (as per section 12.14)
- Further details of the AE, if any.

*The investigator should attempt to establish a diagnosis of the event based on signs, symptoms, and/or other clinical information. In such cases, the diagnosis should be documented as the AE/SAE and not the individual signs/symptoms.

For the recording of signs and symptoms, the subject will be required to report spontaneously any AEs as well as the intensity of these events. In addition, each subject will be asked by the investigator for AEs during vital

Protocol for clinical study of Brequinar

Protocol No.: 21-VIN-0372

Version No.: 2.1; Dated: 29 Dec 2021

Supersedes: 02; Date of Supersedes: 30 Sep 2021

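### No rule requires enrolment to pause or the DSMB to convene after one treatment-related death on active drug, although that death already bars the cohort from being declared safe

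*Combined protocol and SAP*

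**What the plan says.** All references are to protocol Version 2.1; Version 01 carries the same rules.

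- **Declaring a cohort safe (3.1 and 12.9, Safety Criteria).** The first condition is "No toxic deaths (deaths judged by the investigator to be related to either study drug"). The list is read once all Day 15 results are in. Under 9.1, meeting these criteria is the condition for escalating and for choosing the expansion dose.
- **Individual stopping (12.9).** Two kinds of subject come off treatment: those with a Grade 3 toxicity judged related, and those with a Grade 4 toxicity of any cause ("Subjects who develop a Grade 4 toxicity, regardless of relatedness to study drug, are to be permanently discontinued from study treatment"). Section 12.12 grades a fatal event as Grade 5, which neither criterion names.
- **Cohort stopping (12.9).** The CRO physician "will determine if a cohort meets Cohort-level Stopping Criteria prior to completing the 16 subjects". The limbs are at least three "brequinar-treated or combination-treated subjects meet the individual stopping criteria", or at least five "brequinar-treated or combination-treated subjects develop a Grade 3 or higher AE regardless of relationship to study drug".
- **DSMB (9.2 and synopsis).** "The DSMB will be convened and enrollment suspended if Cohort-Level Stopping Criteria are met". Then: "The DSMB may allow the enrollment to resume following their review if safety criteria are met". The minimum DSMB reviews are before the start, between Part 1 and the expansion, and at the end of the study. Routine meetings do not suspend enrolment.
- **Other powers.** Section 12.10 allows suspension or termination according to how serious the SAEs are. Section 9.12 gives the investigator a right to discontinue, and lets the ethics committee or regulator ask for termination. Section 9.1 says that a DSMB finding that a cohort is unsafe stops later cohorts.

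**The concern.** The protocol tolerates no related death when it decides whether a dose is safe, but that test governs escalation and the expansion dose, not continued enrolment at the current dose. Continued enrolment is governed by the cohort stopping counts, and one related death does not reach them. Followed literally, the plan lets new subjects start a dose that can no longer be declared safe, with no required pause and no required DSMB review.

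This matters because section 5.5 says that the combination has never been given clinically and that its bleeding risk relative to either drug alone is unknown. The same section reports that brequinar toxicity in cancer patients on higher doses was sometimes fatal. In Part 1 the exposure is the remainder of one 16-subject cohort. In the expansion it could be the remainder of about 48 subjects, all on brequinar with or without dipyridamole (9.1).

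**Working it through.** **1. Design figures.** Part 1 is 4 × (8 + 4 + 4) = 64 subjects, which matches the stated total. Each cohort has 8 + 4 = 12 subjects on active drug. The expansion has 32 + 16 = 48, all active. No power calculation exists to reproduce.

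**2. Deaths scored against the mandatory trigger, with no other qualifying event.**

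| Related deaths on active drug | Limb 1 (needs 3) | Limb 2 (needs 5) | Suspension required? |
|---|---|---|---|
| 1 | 0 literally; 1 if the subject also met a Grade 3 or 4 individual criterion, or if Grade 5 is read in | 1 | No |
| 2 | 0 to 2 | 2 | No |
| 3 | 0 to 3 | 3 | Only on the generous reading |

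A death could complete a threshold if two other subjects already met the individual criteria, or four already had Grade 3 or higher events. Alone it does not.

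**3. Scope.** The cohort criteria operate before a cohort reaches 16 subjects. The expansion is described as added to a cohort that has already been completed and passed, so the wording does not clearly carry over.

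**4. How many could still be enrolled, given a death.** Let n be the active subjects, k the position of the subject who dies (uniform on 1 to n), and L the active subjects who enter before the death is reported. The mean of max(0, n − k − L) is:

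| | L = 0 | L = 2 | L = 4 |
|---|---|---|---|
| Part 1 cohort, n = 12 | 5.50 | 3.75 | 2.33 |
| Expansion, n = 48 | 23.50 | 21.56 | 19.71 |

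**5. Allowing for how rare a death may be.** The documents give no related-death rate for the combination. Section 5.4 reports no deaths in either earlier COVID-19 study, so 0 of 15 + 56 = 71 on brequinar, described as 100 mg for 5 days and without dipyridamole. The one-sided 95% upper limit is 1 − 0.05^(1/71) = 4.1%. I therefore assume p = 0.5%, 1% and 2% per active subject. The chance of at least one related death is 1 − (1 − p)^n. The expected number enrolled after the first one, averaged over all cohorts with or without a death, is the sum over k of p(1 − p)^(k−1) × max(0, n − k − L).

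| Assumed p | Part 1: chance of a death | Part 1: expected, L = 0 / L = 4 | Expansion: chance of a death | Expansion: expected, L = 0 / L = 4 |
|---|---|---|---|---|
| 0.5% | 5.8% | 0.33 / 0.14 | 21% | 5.2 / 4.4 |
| 1% | 11.4% | 0.64 / 0.27 | 38% | 9.7 / 8.3 |
| 2% | 21.5% | 1.24 / 0.54 | 62% | 17.0 / 14.6 |

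At these rates the present limb 1 would seldom respond to deaths alone. Even with Grade 5 read in, the chance of three or more deaths in a Part 1 cohort that has had one is 0.05%, 0.18% and 0.71%.

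Steps 4 and 5 give upper figures at each assumed rate and lag, because they suppose that nobody uses a discretionary power.

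**The case against.** The protocol is not defenceless, and much of the case against stands.

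- **Discretion exists and would probably be used.** "An independent, unblinded study physician (from CRO) will assess each cohort for safety". SAEs go to the regulator, sponsor and ethics committee within 24 hours (if required), the study can be suspended on SAE seriousness, and the DSMB schedule is only a minimum. A reader might infer that the protocol allows escalation after a related death, or has no means of pausing. The documents support neither: escalation is blocked and a pause is available. What is missing is an obligation.
- **The Part 1 effect is small and falls with reporting lag.** If eight active subjects enter before the report, the mean number still to come, given a death, is (3 + 2 + 1)/12 = 0.5.
- **The expansion starts from a better position.** It opens only after a cohort with no related death, a DSMB review and regulator approval, so the higher assumed rates are less plausible there. None of these adds a pause rule once it is open.
- **The fatal toxicity in 5.5 comes from another setting.** Oncology oral dosing reached 950 mg/m² twice weekly (5.2), against 50 to 200 mg daily for 5 days here, with platelet and bleeding exclusions.
- **A trigger with no arm limit would misfire.** The investigator is blinded, and an event rated Possible counts as related even when the disease could explain it (12.13). A COVID-19 death on placebo could then halt the trial. The existing criteria count only active-treated subjects, and a new rule should do the same.
- **Resumption is a wider problem.** One might infer that the 9.2 resumption condition is a defect peculiar to deaths. It is not: three related Grade 3 toxicities would also fail the Safety Criteria, so the condition could not be met then either. Section 12.9 also says that the cohort takes no more subjects, while 9.2 lets it reopen.

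**Conclusion.** The point holds as a gap between mandatory and discretionary action. One related death on active drug, and likewise two, requires neither a pause nor a DSMB meeting, although the first already disqualifies the cohort from being declared safe. This follows from the text and needs no assumed rate.

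The size does rest on assumptions. In Part 1 the expected consequence is about 0.1 to 1.2 active subjects per cohort at assumed rates of 0.5% to 2%. The expansion matters more, because 48 active subjects are involved and the stopping criteria do not clearly apply. Its figures are illustrative, and the upper end is unlikely for a dose that has passed the gate.

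A stronger conclusion, that the thresholds of three and five are wrong or that sites would in practice carry on enrolling, is not supported. I rate this a cheap improvement of low to moderate severity, justified by patient safety at little cost.

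**What to change.** 1. **Add a separate rule in 3.1 and 12.9**, outside the 16-subject lead-in and stated to cover every Part 1 cohort and the expansion: *Any death judged by the investigator to be related to either study drug, in a subject confirmed by the unblinded CRO physician to have received brequinar or the combination: enrolment is suspended immediately and the DSMB is convened; enrolment resumes only on the DSMB's recommendation.*
2. **Repair the resumption clause in 9.2 and the synopsis for all suspensions.** Replace the Safety Criteria condition with resumption at that dose on the DSMB's recommendation after review. State that a cohort failing the Safety Criteria still cannot be declared safe or escalated from. Bring the 12.9 bar on further enrolment into line with this.
3. **Name Grade 5 beside Grade 4** when counting subjects toward the threshold of three.

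The thresholds of three and five, and the handling of single Grade 3 events, can stay. The cost is wording in 3.1, 9.2 and 12.9, with no new data or patients. The downside is a possible ad hoc DSMB call and an enrolment pause whose length depends on that review.

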12.10 Serious Adverse Events (SAEs)

A serious adverse event is any untoward medical occurrence during a study which satisfies one or more of the following conditions:

- resulting in death or
- permanent disability, or
- hospitalisation of the trial subject, or
- prolongation of hospitalisation, or
- significant disability, or
- incapacity, congenital anomaly, birth defect ,or
- life threatening event.

The term ‘Life threatening’ refers to an event in which the subject was at immediate risk of death at the time of event. It does not refer to an event which may have caused death if it was more severe.

The Investigator will be responsible to report all SAE to the central regulatory (e.g. DCGI-Central Licensing Authority), Sponsor's representative and respective Ethics Committee within 24 hours of SAE occurrence/knowledge of occurrence if required. Investigator will be responsible for reporting the detailed report to the local regulatory (e.g. DCGI), chairman of the Ethics Committee and the head of the institution where the trial has been conducted within 14 days of SAE occurrence if required. Each AE will be evaluated for duration, severity, action taken, outcome and association with Investigational Medicinal Product. The study may be suspended or terminated depending upon the seriousness of SAEs.

Protocol for clinical study of Brequinar
Protocol No.: 21-VIN-0372
Version No.: 2.1; Dated: 29 Dec 2021
Supersedes: 02; Date of Supersedes: 30 Sep 2021

12.11 Reporting and Follow-up

The investigator must complete SAE form, verify the accuracy of the information recorded in corresponding source documents, and send a copy (by fax /mail) to sponsor/representative/CRO.

Investigator:

The investigator shall report all serious adverse events (SAE) to the central licensing authority (DCGI), the Sponsor/CRO and chairperson of ethics committee within 24 hour of SAE occurrence, if required.

The investigator shall report all SAE after due analysis to the central licensing authority (DCGI), chairperson of ethics committee and head of the institution where the trial has been conducted within fourteen days of SAE occurrence, if required. Subsequent follow-up information shall be reported to all stakeholders as mentioned above.

In case, Investigator fails to report any SAE within stipulated period, the investigator shall have to furnish the reason for the delay to the satisfaction of central licensing authority along with the report of SAE.

Sponsor or Sponsor's Representative:

In case of SAE the Sponsor and/or CRO will be responsible for reporting the due analysis report of SAE to chairman of the Ethics Committee, the central licensing authority and the head of the institution where the trial has been conducted within 14 days of SAE occurrence, if required.

Note: In case if SAE occurrence time and reporting time by subject to investigator is not same, investigator may fail to report such serious adverse event within the stipulated period. In such case Investigator shall have to furnish the reason for the delay to the satisfaction of the central licensing authority along with the report of the serious adverse event.

Name of the sponsor representative:

[name]

E-mail: [contact]

Sponsor Medical Monitor:

[name]

E-mail: [contact]

CRO contact details:

Veeda Clinical Research Ltd.

Protocol for clinical study of Brequinar
 Protocol No.: 21-VIN-0372
 Version No.: 2.1; Dated: 29 Dec 2021
 Supersedes: 02; Date of Supersedes: 30 Sep 2021

E-mail: [contact]

[contact]

Follow-up of Adverse Events:

All AEs (serious or not) will be followed to resolution (the subject's health has returned to his/her baseline status or all variables have returned to normal or clinically acceptable level), an outcome is reached, stabilization (the Investigator does not expect any further improvement or worsening of the event), or the event is otherwise explained regardless of whether the subject is still participating in the study. Where appropriate, medical tests and examinations will be performed to document resolution of event(s).

The Investigator should institute any supplemental investigations of SAE based on their clinical judgment of likely causative factors.

If required, a follow-up report including all relevant new or reassessed information (e.g., concomitant treatment, medical history) obtained on the SAE will be prepared and same will be marked "Follow-up report". Follow up reports are to be sequentially numbered to allow tracking. These reports will be sent to the sponsor/CRO.

Adverse events occurring between informed consent and the last visit

The investigator should follow up on all AEs which occurred from signature of study-specific informed consent until the last visit of the subject, at which point the outcome assessment is documented in the CRF.

Ongoing serious adverse events at the time of last visit

For any SAEs still ongoing at the time of last visit considered to be related to IMP, the investigator should continue to follow-up until the SAE has resolved or has stabilized / is judged permanent for SAEs, and for up to 30 days after the last visit of subject for non-related SAEs. Where appropriate, medical tests and examinations will be performed to document resolution of event(s). The investigator should send SAE follow-up reports including all relevant new or reassessed information (e.g., concomitant treatment, medical history) obtained on the SAE /pregnancy to the sponsor/CRO.

If a subject dies during participation in the study and an autopsy is performed, a copy of the report must be submitted.

Serious adverse events occurring after the last visit

Any SAEs experienced after the last visit should only be reported to sponsor if the investigator suspects a causal relationship to study treatment. The investigator must report the SADR to recipients as per the 'SAE Reporting' section 12.10.

Protocol for clinical study of Brequinar
 Protocol No.: 21-VIN-0372
 Version No.: 2.1; Dated: 29 Dec 2021
 Supersedes: 02; Date of Supersedes: 30 Sep 2021

Pregnancy Reporting:

Pregnancy recorded for any trial participant after study drug administration should be reported immediately to the sponsor/representative. The subject will be withdrawn from the trial and every effort will be made to gather information regarding the pregnancy outcome until 8 weeks post-partum/termination of pregnancy. It will be the responsibility of the Investigator to obtain this information. Pregnancy recorded after screening but before randomization will be reported and subject will be withdrawn from the study and further follow up will not be done. In case of pregnancy, separate pregnancy form should be filled. Cases of pregnancy exposure associated with SAE and/or abnormal pregnancy outcome should be reported as per SAE reporting timelines. If any congenital anomaly is observed in offspring then the follow up should be conducted till six months after birth, if applicable.

Ethics Committee Timelines for Reporting of SAE:

In case of SAE, the Ethics Committee shall forward its report along with its opinion on the financial compensation (if any) to the licensing authority within 30 days of the occurrence of the SAE, if required.

12.12 Classification of Severity of Adverse Event

Adverse event will be assessed for onset time, occurrence (single or repeat) and intensity. In terms of grade,

Grade 1: Mild; asymptomatic or mild symptoms; clinical or diagnostic observations only; intervention not indicated.

Grade 2: Moderate; minimal, local or noninvasive intervention indicated; limiting age-appropriate instrumental ADL*.

Grade 3: Severe or medically significant but not immediately life-threatening; hospitalisation or prolongation of hospitalisation indicated; disabling; limiting self care ADL**.

Grade 4: Life-threatening consequences; urgent intervention indicated.

Grade 5: Death related to AE.

*Instrumental Activities of Daily Living (ADL) refer to preparing meals, shopping for groceries or clothes, using the telephone, managing money, etc.

**Self care ADL refer to bathing, dressing and undressing, feeding self, using the toilet, taking medications, and not bedridden.

